220 great deal better) where subjects will check an answer that best describes their current
221 perceived status since injury onset to time of follow up. Meaningful patient improvement/
222 deterioration (on a 15 point scale) is considered to be >5 or <-5 .^{7,23} See Appendix A
223

224 Patient Specific Functional Scale (PSFS): The PSFS is a self-report questionnaire
225 assessing pain, instability and activities of daily living (ADLs). The MID for the PSFS
226 (on a scale from 0 to 10) ranged from 1.3 (small change) to 2.3 (medium change) to 2.7
227 (large change). The PSFS is a reliable and valid tool for assessing outcome in Shoulder
228 Injuries. ⁶ See Appendix A

231 Shoulder Pain and Disability Index (SPADI): The SPADI is a self-report questionnaire
232 assessing pain and disability. The MID for the SPADI (on a 100 point scale) is 13.2. The
233 SPADI is a reliable and valid tool for assessing outcome in shoulder injuries.^{48,49}
234 See Appendix A

236

237

238

239 **3. OBJECTIVES AND SPECIFIC AIMS**

240

241 Objectives:

242

- 243 1.) To determine if the addition of upper quarter TDN to a rehabilitation protocol is more
244 effective in improving range of motion and functional movement when compared to a
245 rehabilitation protocol alone after shoulder stabilization surgery.
- 246 2.) To determine if the addition of upper quarter TDN to a rehabilitation protocol is
247 more effective in decreasing pain than a rehabilitation protocol alone after shoulder
248 stabilization surgery.

249

250 **4. MEDICAL APPLICATION/ MILITARY RELEVANCE**

251

252 TDN is becoming an increasingly common intervention and is widely used among
253 military musculoskeletal providers. Providers claim many benefits from this intervention to
254 include myofascial pain relief and myofascial tension release resulting in improved joint
255 dynamics, range of motion, and flexibility. There are many studies available showing the
256 benefits of this intervention treating myofascial pain.^{24, 25, 26, 27} By contrast, there is a
257 relatively small amount of literature examining the claim of improved range of motion, and
258 to date, only one study has been done to evaluate the benefit of TDN in a postoperative
259 setting.⁸ In case studies by Mason et al, and Dembowski et al, patients receiving TDN
260 demonstrated good improvement in range of motion and demonstrated improved functional
261 movement patterns.^{26, 28}

262

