504 BASELINE DEMOGRAPHIC COLLECTION AND EVALUATION – POST OP DAY ~7 505 Subject recruitment

506 Subjects will be screened for inclusion/exclusion criteria.

507 Subjects will be given a random numeric identifier.

508 All data will be recorded and stored by individual numeric identifier. Group assignment will
509 be kept separate and will only be known by PI or AI.

510 Subjects meeting all entrance criteria, to include standardized physical exam, will be
511 consented, numeric identifier given, and group assignment provided. Demographic
512 information will be recorded to include age, gender, duration and location of symptoms. The
513 physical exam will be in accordance with the post-operative protocol and is standard of care
514 after these procedures. Elements may include evaluation of neurological status,
515 neurovascular integrity, wound healing, and assessment of joint mobility. Data from the
516 initial physical exam is only used for clinical purposes. Both the experimental and control
517 groups will receive physical therapy in accordance with the post-operative protocol until their
518 4 week follow up. No TDN will be performed at this time post-operatively, baseline
519 demographics only.
520
521
522

523
524
525 4 WEEKS POST-OPERATIVE:
526 Initial Data Collection
527 The outcome assessor performing data collection and measurements will remain blinded to
528 group assignment. In both the experimental and control groups, they will test and record
529 ROM of glenohumeral internal rotation, external rotation, flexion, and functional movement
530 of the shoulder. Each subject will complete the Global Rating of Change survey (GROC),
531 Patient Specific Functional Scale (PSFS), and Shoulder Pain and Disability Index (SPADI).
532 Subjects will be asked to report compliance with home exercise program by presenting his or
533 her exercise log. Pain level will be recorded using the NPRS. No TDN will be performed at
534 this time post-operatively, data collection only.
535
536 EXPERIMENTAL GROUP TDN TREATMENTS #1-4, 4-8 WEEKS POST-OPERATIVE
537 TDN will be performed to all detected TPs in experimental group only by PI or AI's. As part
538 of the standard course of treatment, both the experimental and control groups will participate
539 in supervised rehabilitation in accordance with the post-operative rehabilitation protocol
540 throughout this time period.
541
542 8 WEEKS POST-OPERATIVE
543 Follow Up Data Collection

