580 administered, if any. As appropriate, include the validity and reliability of the instruments.
581 For subject's confidentiality protection, outline the procedure for coding, recording, storing
582 and protecting the data. Provide a copy of data collection sheets, case report forms, survey
583 forms/questionnaires/instruments, and/or a copy of the author's permission granting the use
584 of the instruments in the *Appendix Section 20*.

585

586 All data will be collected through survey questions and direct researcher measurements.

587

588

589

590

591 Data collected and Time Points

SURVEY DATA	OBJECTIVE MEASUREMENTS
Age -baseline demographic questionnaire	Glenohumeral Internal Rotation - initial data collection, at each follow up
Gender -baseline demographic questionnaire	Glenohumeral External Rotation - initial data collection, at each follow up
Duration of symptoms -baseline demographic questionnaire	Glenohumeral Flexion - initial data collection, at each follow up
Numeric Pain Rating Scale (NPRS) for shoulder pain -baseline demographic questionnaire - initial data collection, at each follow up	Functional Range of Motion Test - initial data collection, at each follow up
	Global Rating of Change (GROC) -at each follow up
	PSFS -initial data collection, at each follow up
	SPADI -initial data collection, at each follow up

592

593 Study Variables

INDEPENDENT VARIABLES	DEPENDENT VARIABLE
Group Assignment (2 Levels) 
 - Experimental - Control 	Shoulder Range of Motion 
 -Internal Rotation (degrees) - External Rotation (degrees) - Flexion (degrees) -Functional Movement Test
Time (4 Levels) 
 - Week Four - Week Eight - Week 12 - Month Six 	Shoulder pain (NPRS) 
 -with internal rotation - with external rotation - with flexion - with functional movement test
	GROC
	PSFS
	SPADI

594

595

596 Data Collection/Confidentiality

597 Subjects will sign the consent forms but no identifiable information will be on data collection
 598 forms. Each of the subjects will be randomly assigned a subject identification number from
 599 1-38 upon entrance into the study and subsequently given consent forms and survey/data
 600 collection forms with the corresponding number. Each number assigned will only be used
 601 once.

602 All subject information and data collection forms will be kept behind double locks: in

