1. **Global Rating of Change score:** To assess overall change from initial presentation, the GROC will be recorded at each follow up visit. This score is rated from -7 to +7 where subjects will select an answer that best describes their current perceived status since injury onset.^{23,45}
2. **PSFS:** The PSFS is a self-report questionnaire assessing pain, instability and activities of daily living (ADLs).⁶
3. **SPADI:** The SPADI is a self-report questionnaire assessing pain and

648 disability.^{48,49}

649 4.

650

651 6.4.2 Data analysis

652

653 Descriptive statistics will be provided. Data analysis will be performed with statistical
654 analysis software R version 3.1.2. A 2x4 repeated measures ANOVA with Sidak's post hoc
655 testing will be used with time as the within-subjects factor and group (control or TDN) as the
656 between-subjects factor. Alpha will be = .05.

657

658 6.4.3 Safety Monitoring and Analysis Plan.

659 For this study, continuous assessment of participant's response to treatment will be
660 performed, especially their response to dry needling techniques. If the participant experiences
661 soreness greater than expected or has hematoma develop increasing in size then needling
662 techniques will be discontinued. At any time the subject can elect to discontinue participation
663 in the study and will continue with standard of care treatment.

664

665 6.4.4 Sample Size Estimation

666

667 30-50 status post shoulder stabilization surgery meeting inclusion and exclusion criteria will
668 be recruited for this study. A priori sample size calculation using G Power 3.1.2 was
669 performed and it was determined the required sample size would be 34 subjects. This sample
670 size provides 80% power to detect an effect size of 1.0 at the eight week follow-up with an
671 alpha level of .05. To account for a potential 10-15% of subjects lost to follow-up, 38
672 subjects is the goal for recruitment.¹⁴ Multiple prior studies on TDN of upper quarter
673 musculoskeletal disorders have reported very large changes (effect sizes > 1.5) in range of
674 motion after TDN.^{20,27}

675

676 6.5 Reporting Adverse Events

677

678 6.5.1 Expected Adverse Events from Research Risks and Reporting Describe the
679 expected adverse events from research risks using the following categories (the event
680 rates may be derived from your clinical experience or literature).

681

- Rare but serious (Event Rate < 1%):

Collapsing Lung

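### The GROC is given two starting points, neither of them the start of needling, and the sections disagree on whether it is collected at week 4

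*Combined protocol and SAP*

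**What the plan says.** **Starting point of the rating.** The GROC entry in 6.4.1 opens with "To assess overall change from initial presentation, the GROC will be recorded at each follow up visit". The next sentence describes a scale from -7 to +7 "where subjects will select an answer that best describes their current perceived status since injury onset". The instrument description in 2.3 also uses the injury: "perceived status since injury onset to time of follow up". For meaningful improvement or deterioration, 2.3 gives this rule: "deterioration (on a 15 point scale) is considered to be >5 or <-5".

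**Start of needling.** Section 6.3.2 places treatments 1-4 between weeks 4 and 8 and states that none is given at the 4-week data collection. Randomization is at 0-7 days after surgery (2.3), and both arms follow the same rehabilitation until week 4 (6.3.2).

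**Collection times.** The data-collection table in 6.3.4 has "Global Rating of Change (GROC) -at each follow up". The PSFS and SPADI rows of that table also name the initial data collection; the GROC row does not. The 4-week visit text in 6.3.2 nevertheless says "Each subject will complete the Global Rating of Change survey (GROC" (the sentence goes on to the PSFS and SPADI). The 6.3.5 timeline marks the GROC at Baseline, 4, 8 and 12 weeks, and 6 months.

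**Analysis.** The study-variables table in 6.3.4 lists the GROC as a dependent variable under a four-level time factor: weeks 4, 8 and 12, and month 6. Sections 6.4 and 6.4.2 give one 2x4 repeated measures ANOVA with Sidak post hoc tests and no separate analysis for the GROC.

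**The concern.** A transition rating means something only relative to its starting point, and here the starting point is stated in two ways. From injury onset, the rating covers the injury, the operation and the first weeks of rehabilitation. From initial presentation, if that means the enrolment visit at about day 7, it still covers the weeks before needling. In both cases, part of each rating describes a period in which the arms received the same care.

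Three things are at stake. Variation between subjects in pre-needling recovery adds noise to the comparison and uses up part of a bounded scale. A subject in either arm may pass the >5 threshold through surgery and routine rehabilitation alone. And the sections do not settle whether a week-4 rating will exist, which decides what model can be fitted.

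**Working it through.** **1. The plan's own figure.** Section 6.4.4 gives 34 subjects for 80% power, effect size 1.0 at week 8 and alpha .05. A two-sided two-sample t-test needs 16.71 per arm, so 17 per arm and 34 in total, with power 80.7%. The figure reproduces. It names no outcome, and the sentence supporting it cites range of motion. No figure in the documents concerns the GROC.

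**2. Effect of an early starting point on the comparison.** Write the week-8 rating as A + B, where A is change from the starting point to week 4 and B is change from week 4 to week 8.
- Mean: A arises before needling and under the same care, so its expectation is equal in both arms. This takes it that knowing the allocation does not itself change ratings before week 4. The expected group difference in A + B is then the difference in B: no bias.
- Spread: if A and B are uncorrelated and r = Var(A)/Var(B), a standardized effect d on B becomes d/√(1 + r) on A + B.
- Contrast: week 8 minus week 4 is (A + B) - A = B, so r drops out if a week-4 rating with the same starting point exists and the scale does not saturate.

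**3. Illustration.** Here r is assumed, d = 1.0 on B and there are 17 per arm. The last two columns simulate a rounded rating bounded at -7 and +7 (20,000 runs). They assume SD 1.5 and effect 1.5 for B, mean B of 2 in controls, and mean week-4 rating 0 or +3.

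| r | d/√(1 + r) | Power by formula, week 8 alone | Simulated power, week 8 alone (mean 0 / +3) | Simulated power, week 8 minus week 4 (mean 0 / +3) |
|---|---|---|---|---|
| 0.25 | 0.89 | 71.5% | 70.8% / 65.9% | 78.1% / 70.8% |
| 0.5 | 0.82 | 63.6% | 62.4% / 57.7% | 77.9% / 68.3% |
| 1 | 0.71 | 51.6% | 51.4% / 46.1% | 77.2% / 61.8% |
| 2 | 0.58 | 37.2% | 36.5% / 32.2% | 75.7% / 51.7% |

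A rating anchored at week 4 gave about 79% throughout. With no effect, rejection rates stayed between 4.6% and 5.2%. With a mean week-4 rating of +3, the 1.5-point difference shrank to between 1.02 and 1.15 points through the ceiling.

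**4. The threshold.** On a 15-point integer scale, >5 means +6 or +7. Under the simulation's assumed means of +3 before and +2 after week 4, the average control rating before rounding and bounding is 3 + 2 = +5, one point short of the threshold, with no needling. From a week-4 starting point it would be +2.

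**5. The schedule against the model.**
- 6.3.4 data-collection table: weeks 8 and 12 and month 6, so 2 x 3; a 2x4 cannot be fitted.
- 6.3.2 visit text: weeks 4, 8 and 12 and month 6, so a 2x4 can be fitted.
- 6.3.5 timeline: the same four plus Baseline, which lies outside the four-level factor. If initial presentation is the enrolment visit, a Baseline rating has essentially no interval to describe.

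The two tables of 6.3.4 therefore disagree with each other: one gives the GROC three collection times, the other a four-level time factor.

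**The case against.** Most of the case on the other side stands.

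- A reader might infer that injury, surgery and early recovery confound the needling comparison. They do not: randomization precedes needling, and the simulated type I error stays at its nominal level.
- A reader might infer that the GROC cannot fit the 2x4 ANOVA at all. On the 6.3.2 and 6.3.5 schedules it can, and week 4 then serves as a pre-needling level, as it does for range of motion, NPRS, PSFS and SPADI.
- A reader might infer that subjects are shown two starting points on one form. The documents do not support this. Both descriptions of what the subject answers use injury onset; initial presentation appears only in the sentence on purpose. The form is in Appendix A, which is not in the text available, so its wording cannot be checked.
- The schedule conflict is narrow. Section 6.3.2 itself once calls week 4 a follow-up, so the 6.4.1 wording can include it. The Baseline mark in 6.3.5 is not peculiar to the GROC: PSFS and SPADI are marked there too, and 6.3.4 lists neither at Baseline.
- Perceived change since injury is a legitimate global outcome, and a week-4 starting point has its own recall problem by month 6.

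Three things remain. Section 6.4.1 gives two reference points. The 6.3.4 data-collection table omits a rating that 6.3.2 and 6.3.5 collect. And although the contrast against week 4 would recover much of the lost sensitivity, the plan does not name it, or the group-by-time interaction, as the test for the GROC. Post hoc group comparisons made visit by visit would not subtract week 4.

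**Conclusion.** The point holds as one of sensitivity, interpretation and internal consistency. The reference point is stated in two ways, neither isolates the needling period, and the >5 threshold cannot be read as a response to needling. The plan states that threshold but no responder analysis, so the harm lies in how GROC results would be interpreted. On the follow-ups-only schedule the planned model cannot be run for this outcome; on the other schedule it can.

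The power figures above might tempt a reader to say that the trial loses a quarter to a half of its power. The documents do not support that. The variance ratios, SD, effect and means are all assumed, the largest losses belong to an unadjusted week-8 comparison, and the sample size was not justified on the GROC. The figures show direction only.

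The GROC is one of three secondary outcomes and does not appear in the section 3 objectives. PSFS and SPADI already give self-reported function with a week-4 value. Minor to moderate.

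**What to change.** Use one starting point everywhere, on the Appendix A form and in 2.3 and 6.4.1: *since your 4-week post-operative visit*. Collect the GROC at 8 weeks, 12 weeks and 6 months only. To match, remove it from the 4-week visit text in 6.3.2 and from the Baseline and 4-week columns of 6.3.5, keep the 6.3.4 data-collection row, and note in the study-variables table that the GROC has three time levels. State in 6.4 and 6.4.2 that it is analysed as 2 groups by 3 times.

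If the investigators prefer change since injury, the alternative is to state injury onset throughout, keep the week-4 rating and add it to the 6.3.4 row, drop the Baseline rating, and base the GROC inference on the group-by-time contrast against week 4. The >5 threshold should then not be described as response to needling.

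Either route costs only wording and adds no visits. The downside of the first is that at month 6 subjects must recall their state about five months earlier, though that is more recent than injury onset. The choice has to be made before the first rating is taken, because a rating given against one period cannot be re-anchored afterwards.

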90 stabilization surgery. Measurements of the aforementioned dependent variables will be taken
91 at time intervals of four weeks, eight weeks, 12 weeks, and six months post-operatively. It is
92 hypothesized that the inclusion of dry needling will result in an increase in range of motion,
93 increase in functional movement, and decrease in pain at an accelerated rate when compared
94 to rehabilitation alone. Findings will potentially lead to insights as to the benefit of applying
95 this intervention to additional body regions.
96

97 **2.2 Research Design**

98 The research design will be a single-blinded randomized controlled trial.
99

100 **2.3 Methodology /Technical Approach**

101 30-50 subjects at least four weeks after shoulder stabilization surgery will be
102 randomized into two groups (one experimental group and one control group). Subjects in the
103 experimental group will receive Trigger Point Dry Needling (TDN) intervention with
104 standard rehabilitation protocol (Appendix A) while subjects in the control group will receive
105 the same standard rehabilitation protocol without TDN. The experimental group will receive
106 trigger point dry needling one time per week for four to six weeks in addition to the standard
107 rehabilitation protocol. The control group will receive only the standard rehabilitation
108 protocol. Baseline measurements will be taken at approximately four weeks post operatively,
109 and subsequent measurements will be recorded at eight weeks, 12 weeks, and six months.

110 All patients who have undergone a shoulder stabilization procedure will be invited to
111 participate. Description of the study and informed consent will take place prior to
112 randomization. Concealed randomization will take place 0-7 days post-operatively.

113 At 4 weeks post-operatively, the following assessment tests will be undertaken:
114 supine shoulder flexion, supine shoulder external rotation, supine shoulder internal rotation,
115 functional movement testing, functional outcome measures, and the numeric pain rating
116 scale.^{1,2,3} Those subjects in the 'experimental group' will receive manual palpation of all
117 upper quarter muscles, including the cervical and thoracic spine region, to detect the presence
118 of myofascial trigger points (TPs). Dry needling will be performed to all detected TPs by a
119 provider trained and experienced in TDN.

120 In addition to the TDN intervention, the experimental group subjects will undergo a

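### Section 6.4.2 names no sphericity correction or covariance structure for the 2x4 repeated measures ANOVA; if correlation decays or spread changes across visits, an uncorrected group-by-time test would run at about 6%-8% instead of 5%.

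*Combined protocol and SAP*

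**What the plan says.** The inferential plan is essentially one sentence. It appears in section 6.4 (Statistical Consideration) and again in 6.4.2 (Data analysis): "A 2x4 repeated measures ANOVA with Sidak's post hoc" ... "testing will be used with time as the within-subjects factor and group (control or TDN) as the" between-subjects factor. Section 6.4.2 adds the significance level: "between-subjects factor. Alpha will be = .05". The software is R 3.1.2.

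The four levels of time are weeks 4, 8 and 12 and month six (sections 2.1 and 6.3.4). Neither section mentions sphericity, a test for it, an epsilon correction, a multivariate alternative, or a mixed model with a stated covariance, and nothing on these points appears elsewhere in the text available for review. The error term for the Sidak comparisons is not stated. No SDs or between-visit correlations are given for any outcome.

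Section 6.4.4 bases the sample size on a single visit. It requires 34 subjects, and that "size provides 80% power to detect an effect size of 1.0 at the eight week follow-up with an" alpha of .05. The recruitment goal is 38.

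**The concern.** The ordinary F tests for time and for group-by-time have their stated level only under sphericity, meaning that the difference between any two visits has the same variance. Two features of this trial make that doubtful. The gaps between visits are 4, 4 and about 14 weeks, so any fading of correlation with time makes the long-gap differences more variable. Several primary outcomes are also bounded (pain 0-10, functional tests scored with 0 as best), so spread may shrink as patients recover.

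The affected test matters. Section 2.1 hypothesises faster improvement with needling. Week 4 is measured before any needling (section 6.3.2), so the group main effect averages in a pre-treatment visit. Group-by-time is therefore the natural test of the hypothesis, and it is one of the tests that depend on sphericity. With no rule in the plan, the choice to correct or not can be made after the data are seen.

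**Working it through.** **Inputs from the documents.** Two groups, four visits, alpha .05 (6.4.2); 34 subjects, effect size 1.0 at week 8, 80% power, 10-15% loss (6.4.4).

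**Assumptions.** 1:1 allocation (ratio not stated), six months taken as 26 weeks, and all within-subject covariances.

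**1. The plan's own figure.** A two-sided, two-sample t-test with d = 1.0, alpha .05 and 80% power needs 16.71 per arm. That rounds up to 17, or 34 in total, with power 80.7%. A one-sided test gives 14 per arm (28), which does not fit. At 10% loss, 34/0.90 = 37.8, or 38, the stated goal; at 15%, 34/0.85 = 40. The sizing therefore reproduces as a two-group comparison at one visit.

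**2. Departure from sphericity: one worked case.** Take equal SDs of 1 and correlation .7 per 4 weeks, so the correlation between visits t weeks apart is .7^(t/4). The variance of a visit difference is 2(1 - correlation):
- weeks 4 and 8, or 8 and 12: 2(1 - .70) = 0.60
- weeks 4 and 12: 2(1 - .49) = 1.02
- weeks 12 and 26: 2(1 - .287) = 1.43
- weeks 8 and 26: 2(1 - .201) = 1.60
- weeks 4 and 26: 2(1 - .141) = 1.72

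Sphericity would make all of these equal. Box's epsilon is [tr(CSC)]² / {3 tr[(CSC)²]}, where S is the covariance matrix and C the 4x4 centring matrix. Here it is 1.741² / (3 × 1.337) = 3.030/4.012 = 0.755.

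**3. Effect on the test level.** The uncorrected test uses F with 3 and 3 × (34 - 2) = 96 degrees of freedom, critical value 2.699. Box's approximation to the true level is P(F(3e, 96e) > 2.699), where e is epsilon. It gives 5.6% at e = 0.9, 6.4% at 0.8, 7.2% at 0.7, 8.1% at 0.6 and 11.0% at the lower bound of 1/3.

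Simulation under no group-by-time effect used 17 per arm and 40,000 trials per row. The Monte Carlo standard error at 5% is √(.05 × .95/40,000) = 0.11 percentage points.

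| Assumed correlation and SDs (weeks 4, 8, 12, 26) | Epsilon | Uncorrected | Greenhouse-Geisser | Huynh-Feldt |
|---|---|---|---|---|
| Constant .5, equal SDs (sphericity) | 1.00 | 4.9% | 4.4% | 4.8% |
| .5 per 4 weeks, equal SDs | 0.87 | 5.6% | 4.5% | 5.0% |
| .7 per 4 weeks, equal SDs | 0.76 | 6.3% | 4.6% | 5.0% |
| .9 per 4 weeks, equal SDs | 0.63 | 7.4% | 4.9% | 5.2% |
| .7 per 4 weeks, SDs 1.5, 1.2, 1, 0.7 | 0.75 | 6.7% | 4.9% | 5.3% |
| .7 per 4 weeks, SDs 2, 1.5, 1, 0.5 | 0.65 | 7.4% | 4.8% | 5.1% |
| .9 per 4 weeks, SDs 2, 1.5, 1, 0.5 | 0.48 | 8.8% | 4.9% | 5.1% |
| Near the lower bound | 0.33 | 11.1% | 5.1% | 5.1% |

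A separate run with SDs 2:1.6:1.3:1 and correlations .5 to .9 per 4 weeks gave 6.1%-7.8% uncorrected.

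**4. What is not affected.** In the same simulations the group main effect rejected 4.9%-5.2% of the time. A week-8 t-test using only week-8 data rejected 4.8%-5.2%.

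**5. Post hoc tests, if a pooled error term is used.** With SDs 2:1.6:1.3:1, the pooled SD is √[(4 + 2.56 + 1.69 + 1)/4] = √2.3125 = 1.52. Relative to the visit's own SD, the standard error is:
- week 4: 1.52/2 = 0.76, understated by 24%
- week 8: 1.52/1.6 = 0.95, understated by 5%
- week 12: 1.52/1.3 = 1.17, overstated by 17%
- six months: 1.52/1 = 1.52, overstated by 52%

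With Sidak over four visits the nominal level per visit is 1 - .95^(1/4) = 1.3%. The actual level would be about 6% at week 4, about 2% at week 8 and under 0.1% at six months.

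**The case against.** The strongest reply is that the plan is silent on sphericity, and silence is not a decision to leave a correction out. A reader might infer that the sponsor intends the uncorrected test; the documents do not say so.

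A reader might also infer that sphericity will certainly fail, so that the 5% level is not delivered. That cannot be shown. No covariances are given, and unequal spacing alone does not break sphericity: with equal SDs and equal correlations epsilon is 1 whatever the gaps, and the level is about 5%. Decaying correlation and shrinking spread are plausible for recovery data, but they are assumptions.

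The reach is limited too. Among the omnibus tests only the within-subject ones are exposed. The sample size rests on a week-8 comparison, which is unaffected if tested with week-8 data.

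It is tempting to add that the time-point standard errors are wrong in both directions. That holds only with a pooled error term and SDs that differ by visit, and neither is established. Even then, the largest understatement falls at week 4, before treatment. Week 8 is off by about 5%, and the six-month error makes that test conservative at the price of power.

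These points stand and set the size of the concern. They do not remove it: the plan does not secure the stated level for the test closest to its hypothesis.

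**Conclusion.** The concern holds as a gap in specification with a modest, conditional effect. If correlation decays at .5 to .9 per 4 weeks, with SDs equal or falling about 2:1, an uncorrected group-by-time test at 17 per arm has a level of about 6%-8%. It reaches about 9% when SDs fall 4:1 with high correlation, about 11% at the mathematical bound for four visits, and about 5% if sphericity holds. The F test for time behaves in the same way. Greenhouse-Geisser brings the group-by-time test to 4.4%-5.1% in every scenario run.

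These figures rest on 1:1 allocation, 34 complete cases, six months read as 26 weeks, normal data and the assumed covariances. They do not show that the trial's overall error rate exceeds 5%, or that the week-8 comparison used for sizing is invalid.

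**What to change.** Amend 6.4.2, and the matching sentence in 6.4, before group assignment is combined with the outcome data.

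- **Minimum change.** Pre-specify the Greenhouse-Geisser correction for the time and group-by-time tests, applied whatever a preliminary sphericity test shows. State that the Sidak between-group comparisons at each visit use that visit's own variance, not a pooled error term.
- **Preferred change.** Replace the ANOVA with a mixed model for repeated measures: group, visit and group-by-visit as fixed effects, unstructured covariance across the four visits, and small-sample degrees of freedom. Take the time-point contrasts from that model with the Sidak adjustment. This needs no sphericity assumption and gives visit-specific variances. It also keeps subjects with a missed visit, whom a standard repeated measures ANOVA drops; section 6.4.4 expects 10-15% loss. That last benefit concerns missing data, and the minimum change is enough for the test level alone.

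The cost is a few sentences in the plan, a few lines of R and slightly fewer effective degrees of freedom. If sphericity does hold, Greenhouse-Geisser is mildly conservative (4.4% against 4.9% in the simulation). The unstructured model estimates 4 × 5/2 = 10 covariance parameters from about 34 subjects, which is why the small-sample degrees of freedom should be written into the plan.
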